#### **2.9.2.3.1. Analysis of the Secondary UPE endpoint in the All-Patients Population at Week 36**

The analysis of the secondary UPE endpoint change from baseline in log-transformed 24-hour UPE in g/day at Week 36 in the all-patients population (baseline 24-hour UPE  $> 1$  g/day) will also be analyzed following the same methods listed above in Section [2.9.2.1](#) for the primary UPE endpoint change from baseline in log-transformed 24-hour UPE in g/day at Week 36 in the high-risk proteinuria group (baseline UPE  $\geq 2$  g/day).

#### **2.9.2.3.2. Analysis of Other Secondary and Exploratory Efficacy Endpoints**

These supportive analyses will be performed in both the high-risk proteinuria groups and the all-patients population.

Proteinuria durability will be evaluated by the time-adjusted area-under-the-curve (AUC) change from baseline in the log-transformed 24-hour UPE between 36 and 48 weeks and between 36 and 72 weeks. The time-adjusted AUC will be calculated as the AUC of the change in the log-transformed 24-hour UPE from baseline over the said time period divided by the time between the first observation and the last observation over the same said time period. Patients who are on study and have not reached the Week-36 visit will be excluded from the analysis. The time-adjusted AUC will be summarized descriptively. Both the geometric-mean ratio relative to the study baseline and the coefficient of variation in percentage will be provided by treatment group for the FAS population.

Natural logarithm transformation will be used to analyze 24-hour UPE, 24-hour uPCR, 24-hour uACR, spot-urine uPCR and spot-urine uACR. Geometric-mean ratio relative to the study baseline will be presented by treatment group and visit for the FAS population. A repeated measures model for the change in the log-transformed value from baseline will be used for analysis. The model will include treatment, time (as a categorical variable for the scheduled timepoints), treatment by time interaction, and randomization strata as fixed effects. Within-patient error will be modelled via an unstructured covariance matrix. The REML method will be used to estimate the model parameters. The difference in least squares (LS) means between the treatment groups and their respective 95% CIs will be estimated for each post-baseline scheduled visit. The LS mean will be estimated with 95% confidence interval (CI) for each treatment group. The ratio of the GMR between the treatment groups will also be estimated with 95% CI.

The time-to-event endpoints will be analyzed by Kaplan-Meier (KM) method for each treatment group for the FAS population. Median time with 95% confidence interval will be provided by treatment group. Log-rank test stratified by the randomization stratum will also be performed.

Change from baseline in RBC/HPF will be summarized descriptively by treatment group and scheduled visit.

#### 2.9.2.4. Other Efficacy Endpoints

All other efficacy endpoints will be analyzed for the FAS population.

Proteinuria durability will be evaluated by the time-adjusted AUC change from baseline in the log-transformed 24-hour UPE between 36 weeks and 48 weeks and between 36 weeks and 72 weeks. The time-adjusted AUC will be calculated as the AUC of the change in the log-transformed 24-hour UPE from baseline over the said time period divided by the time between the first observation and the last observation over the same said time period. All UPE values collected over the said time period, including values collected at unscheduled visits, will be used to calculate the time average. Patients who are on study and have not reached the Week 36 visit will be excluded from the analysis. The time-adjusted AUC will be summarized descriptively. Both the geometric-mean ratio relative to the study baseline and the coefficient of variation in percentage will be provided by treatment group for the FAS population. Multiple imputations with FCS regression method will be used to impute missing log-transformed 24-hour UPE at the scheduled visits from Week 12 to Week 72. The FCS regression method will include the treatment group and the randomization strata as covariates. The time-adjusted AUC will be calculated using the imputed values. The treatment difference will be estimated by an analysis of variance model with treatment and randomization strata as factors using the Rubin's rules with 20 imputations.

Natural logarithm transformation will be used to analyze 24-hour UPE, 24-hour uPCR, 24-hour uACR, spot-urine uPCR, and spot-urine uACR. Geometric-mean ratio relative to the study baseline will be presented by treatment group and visit for the FAS population. A repeated measures model for the change in the log-transformed value from baseline will be used for analysis. The model will include treatment, time (as a categorical variable for the regular scheduled visits), treatment by time interaction, randomization strata as fixed effects, a time-dependent covariate for open-label treatment of narsoplimab as fixed effects, and an AR(1) covariance matrix. The time-dependent covariate is a binary variable that has a value of 0 before the initiation of the open-label treatment and 1 afterwards. It is defined for the placebo-treated group only. The REML method will be used to estimate the model parameters. The difference in LS means between the treatment groups and their respective 95% CIs will be estimated for each post-baseline scheduled visit. The LS mean will be estimated with 95% CI for each treatment group. The ratio of the GMR between the treatment groups will also be estimated with 95% CI. It is noted that the primary analysis of 24-hour UPE is based on the 24-hour UPE up to Week 36 and the time-dependent covariate is not applicable to the primary analysis.

Time-adjusted AUC change from baseline in log-transformed 24-hour uPCR through 36 weeks will be calculated as the AUC of the change from baseline in log-transformed 24-hour uPCR divided by the time from baseline to the last observation on or before Week 36. All 24-hour uPCR values collected from baseline to Week 36, including values collected at additional treatment visits and unscheduled visits, will be used to calculate the time adjusted AUC. Time

adjusted AUC of change in log-transformed 24-hour uPCR will be summarized descriptively. An analysis of covariance with treatment and randomization strata as factors and baseline uPCR as a covariate will be performed. The binary endpoints will be summarized descriptively. Non-responder imputation will be used to impute missing data. Exact 95% confidence intervals for the crude rate will be calculated and a Cochran–Mantel–Haenszel test stratified by the randomization stratum will be performed for the FAS population.

The following time-to-event endpoints will be analyzed by the KM method for each treatment group for the FAS population. If calculable, median time with 95% CI will be provided by treatment group. The HR, CI and p-value will be estimated via Cox regression analysis stratified for the randomization strata and with treatment as the sole class factor.

- Duration of treatment response will include patients in the FAS population who achieve  $\geq 30\%$  reduction from baseline in 24-hour UPE only. Patients who respond but do not relapse during the study will be censored at their last date of 24-hour UPE
- Duration of complete proteinuria remission will include patients in the FAS population who achieve 24-hour UPE  $< 0.3$  g/day only. Patients who achieve complete proteinuria remission but whose 24-hour UPE does not increase to  $\geq 0.3$  g/day during study will be censored at the last date of 24-hour UPE
- Duration of partial proteinuria remission will include patients in the FAS population who achieve 24-hour UPE  $< 1$  g/day only. Patients who achieve partial proteinuria remission but whose 24-hour UPE does not increase to  $> 1$  g/day during study will be censored at the last date of 24-hour UPE

Change from baseline in RBC/HPF will be summarized descriptively by treatment group and scheduled visit.

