14.1.10.3. Analyses of Secondary and Exploratory Efficacy Endpoints

Proteinuria durability will be evaluated by the time adjusted AUC change from baseline in the log-transformed 24-hour UPE between 36 and 48 weeks, and between 36 and 72 weeks. The time adjusted AUC will be calculated as the AUC of the change in the log-transformed 24-hour UPE from baseline over the said time period divided by the time between the first observation and the last observation over the said time period. Patients who are on study and have not reached the Week-36 visit will be excluded from the analysis. The time adjusted AUC will be summarized descriptively. The geometric mean ratio relative to the study baseline, and the coefficient of variation in percentage will be provided by treatment group for the FAS population. A MI with FCS regression method will be used to impute missing log-transformed 24-hour UPE at the scheduled visits from Week 12 to Week 72. The FCS regression method will include the treatment group and the randomization strata as covariates. The time adjusted AUC will be calculated using the imputed values. The treatment difference will be estimated by an analysis of variance (ANOVA) model with treatment and randomization strata as covariates using Rubin method with 30 imputations.

Proteinuria responder durability will be evaluated by the time adjusted AUC 24-hour UPE from 36 weeks to 48 weeks where this time adjusted AUC is < 1 g/day or at least 50% reduced from the baseline 24-hour UPE for the high proteinuria group in the FAS population. Patients who are on study and have not reached the Week-36 visit will be excluded from the analysis. The time adjusted AUC will be calculated using AUC similar to the above. Patients with missing time average will be considered as non-responders (non-responder imputation). Percentage of proteinuria responder durability will be summarized by treatment group. A CMH test stratified by the baseline eGFR level (≥ 30 to ≤ 45 mL/min/1.73 m² and > 45 mL/min/1.73 m²) will be performed. Proteinuria responder durability will also be evaluated similarly by the time adjusted AUC 24-hour UPE from 36 weeks to 72 weeks.

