### **2.9.2.1. Analysis of the Primary UPE Efficacy Endpoint in the High-Risk Proteinuria Group (Baseline UPE $\geq 2$ g/day)**

The primary efficacy endpoint will be based on the natural logarithm transformed 24-hour UPE. Descriptive statistics for the log-transformed 24-hour UPE change from baseline to 36 weeks, the geometric mean ratio (GMR) relative to the study baseline, and the coefficient of variation in percentage will be provided by treatment group for the FAS population.

The primary analysis will be a MMRM analysis on the change from baseline in log-transformed 24-hour UPE at Week 12, Week 24, Week 30, and Week 36. The model will be fitted in SAS via the PROC MIXED procedure. Terms will be included for treatment, time (as a categorical variable for the four timepoints), treatment by time interaction, and randomization strata as fixed effects. Within patient error will be modeled using an unstructured covariance matrix. Log baseline UPE will be included as a covariate in the model. Restricted maximum likelihood method will be used to estimate the model parameters. If the estimation of the model fails, an autoregressive (1) [AR(1)] covariance structure will be used. SAS code will be of the form,

```
PROC MIXED DATA=X METHOD=REML;
  CLASS PATIENT RANDTRT VISIT STRATA;
  MODEL CHG_BL = BASE RANDTRT VISIT RANDTRT*VISIT STRATA
    /DDFM=KR;
  REPEATED VISIT / PATIENT = PATIENT TYPE = UN;
  LSMEANS RANDTRT*VISIT/SLICE=VISIT PDIFF DIFF ALPHA=0.05 CL;
  ODS OUTPUT DIFFS=DIFF LSMEANS=LSMEANS;
RUN;
STRATA: Baseline eGFR level ( $\geq 30$  to  $\leq 45$  mL/min/1.73 m2 and  $> 45$  mL/min/1.73 m2)
```

The difference in least squares (LS) means at Week 36 between the treatment groups and its 95% confidence interval (CI) will be estimated. Two-sided p-value will be calculated. The LS mean at Week 36 will be estimated with 95% CI for each treatment group. The ratio of the GMR between the treatment groups will also be estimated with 95% CI.

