#### **Jump to Placebo Multiple Imputation**

The first approach will employ a control-based multiple imputation [Ratitch 2011] whereby missing observations in both the narsoplimab and placebo groups are imputed using only data observed in the placebo group; as such, this approach reflects a 'jump to placebo (or reference)' analysis. Imputation of values in the placebo arm will assume missing at random (MAR) while imputation of values in the narsoplimab arm will assume missing not at random (MNAR), i.e. as if the patient had been a member of the placebo arm. This approach does not assume a sustained benefit of narsoplimab treatment after discontinuation and limits a post-discontinuation effect to that of placebo. The approach will be implemented as follows:

- Step 1: Non-monotone missing data will be imputed first based on the MAR assumption and a multivariate joint Gaussian imputation model using Markov chain Monte Carlo (MCMC) method as per the MCMC statement in the SAS® PROC MI procedure. As a result, each imputed dataset will only have missing data at the end of patients' records, (a monotone missing data pattern). The MCMC method in the MI procedure will be used with multiple chains (option CHAIN=MULTIPLE), 100 burn-in iterations, and a non-informative prior. A separate imputation model will be used for each treatment arm. The imputation models will include the randomization stratification factors, baseline log UPE and change in log UPE at each time point. In case of non-convergence or non-estimability issues, a ridge prior and a single model will be considered with treatment arm added as explanatory variable to the model.
- Step 2: The remaining, monotone, missing data will be imputed using sequential regression multiple imputation model estimated based on data from the *placebo arm only*. Each sequential regression model (i.e., for imputation of values at a given time point) will include the stratification factors, baseline log UPE, and all previous values of UPE. Missing values at a given time point in placebo and narsoplimab treatment arms will be imputed from the same imputation model, conditional on patient values observed or imputed at previous time points.
- Step 3: The log change from baseline in UPE to each scheduled post-baseline visit will be calculated, based on observed and imputed data. Each of the imputed complete datasets from Step 2 will be analysed with the same MMRM model used for the primary analysis.

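### The time-averaged UPE analyses, the longitudinal proteinuria models and the UPE imputation list no baseline value, which gives up some precision in supportive endpoints

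*SAP*

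**What the plan says.** **Time-averaged UPE.** SAP section 2.1 lists four such endpoints as other secondary endpoints. For the comparison, SAP 2.9.2.4 says: "The treatment difference will be estimated by an analysis of variance model with treatment and randomization strata as factors". Protocol 14.1.10.3 specifies the same form: "analysis of variance (ANOVA) model with treatment and randomization strata as covariates".

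**Imputation for those endpoints.** Missing log UPE from Week 12 to Week 72 is filled in by fully conditional specification (FCS). SAP 2.9.2.4 says: "The FCS regression method will include the treatment group and the randomization strata as covariates".

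**Longitudinal models for change in log UPE, uPCR and uACR.** SAP 2.9.2.3.2 has treatment, time, "treatment by time interaction, and randomization strata as fixed effects", with an unstructured covariance. SAP 2.9.2.4 has a second version that adds "a time-dependent covariate for open-label treatment of narsoplimab as fixed effects, and an AR(1) covariance matrix", and protocol 14.1.10.3 matches that version. None lists a baseline value.

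**Where the plan does use baseline.**
- Primary model, SAP 2.9.2.1: "Log baseline UPE will be included as a covariate in the model". The all-patients Week 36 UPE endpoint follows the same method (SAP 2.9.2.3.1).
- Primary-endpoint imputation, SAP 2.9.2.2: "The imputation models will include the randomization stratification factors, baseline log UPE and change in log UPE at each time point".
- Time-averaged uPCR through Week 36, SAP 2.9.2.4: an analysis of covariance with baseline uPCR. The protocol's time-averaged uPCR analysis has no baseline term.

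**The concern.** Change from baseline is usually correlated with baseline, because patients with a high starting value tend to fall back. If the baseline value is left out, that explained variance stays in the residual.

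The strata terms do not make up for this in the high-risk group. Every patient there is in the 2 g/day or higher UPE stratum, and the primary code reduces the factor to "STRATA: Baseline eGFR level". The strata therefore carry no information on baseline proteinuria in that group.

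The plan is also inconsistent with itself. The repeated-measures models estimate the treatment difference at every scheduled visit, so Week 36 UPE is estimated once with baseline (primary model) and again without it. No reason is given for adjusting one time average (uPCR) and not the higher-ranked ones (UPE).

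At stake is the width of the confidence intervals for the durability objective. These endpoints have no alpha-controlled test, so the estimate and its interval are the evidence.

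**Working it through.** **The plan's own figure.** No power is stated for the time-averaged endpoints. The only UPE sizing is N = 180 for the primary endpoint: SD 0.80, 35% reduction, 95% power, two-sided 5%. Per arm, 2 × (1.960 + 1.645)² × 0.80² / ln(0.65)² = 2 × 12.995 × 0.64 / 0.1856 = 89.6, so 90 per arm and N = 180. This reproduces with ln(0.65) = -0.431. The printed -0.393 would give 108 per arm, which is a separate matter. The two SDs used below, 0.80 (planning) and 0.63 (blinded, high-risk group), come from SAP 1.3.1.

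**Variance removed by adding baseline.** Let s be the SD of log baseline, b the slope of change on log baseline, and SD the unadjusted SD of change. The fraction of variance removed is b² × s² / SD².

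The documents give neither s nor b. Assumed ranges: s from 0.3 to 0.5, b from 0 to -0.5.

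| b, s | SD 0.63 (SD² = 0.3969) | SD 0.80 (SD² = 0.64) |
|---|---|---|
| 0, any | 0% | 0% |
| -0.2, 0.3 | 0.0036 / 0.3969 = 0.9% | 0.0036 / 0.64 = 0.6% |
| -0.35, 0.4 | 0.0196 / 0.3969 = 4.9% | 0.0196 / 0.64 = 3.1% |
| -0.5, 0.5 | 0.0625 / 0.3969 = 15.7% | 0.0625 / 0.64 = 9.8% |

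At the upper end this equals 1/(1 - 0.157) = 1.19, or 19% more patients, with SD 0.63, and 1/(1 - 0.098) = 1.11, or 11% more, with SD 0.80. Both SDs describe the Week 36 change. They stand in for the SD of the time average, which is not given.

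**Imputation.** The FCS step runs over the visits from Week 12 to Week 72, so each missing visit is regressed on the patient's other visits as well as on treatment and strata. A dropout with any post-baseline UPE therefore still contributes their own level. Only a patient with no post-baseline UPE is imputed from treatment and strata alone. As an illustration, take two such patients in the same arm and eGFR stratum, with baselines of 2.1 and 8 g/day. Both are drawn from the same distribution. Subtracting their own baselines then separates their changes by ln(8/2.1) = 1.34 log units on average, purely through the subtraction.

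**Simulation.** Setting: the Week 36 to 72 average in the high-risk group, N = 180, true effect -0.3 on the log scale, s about 0.44, 20 imputations, 400 runs per setting. Mean standard errors:

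| Setting | As planned | Baseline in imputation only | Baseline in analysis only | Both |
|---|---|---|---|---|
| b = -0.5, 20% dropout | 0.0926 | 0.0910 | 0.0860 | 0.0851 |
| b = -0.2, 20% dropout | 0.0877 | 0.0853 | 0.0865 | 0.0845 |
| b = -0.5, 35% dropout, more likely at high baseline | 0.0988 | 0.0957 | 0.0914 | 0.0900 |

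Using baseline in both models cuts the standard error by 8%, 4% and 9%. The imputation model alone accounts for about 2% to 3%. Bias was at most 0.006 in absolute value under every approach. Dropout did not differ by arm in these runs.

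**The case against.** The strongest case against is low consequence. SAP 2.9.1 places these endpoints outside type I error control and calls them supportive. The UPE endpoints that matter most, Week 36 in each population, are already adjusted. An unadjusted comparison of change is unbiased under randomization. The gain rests on assumed inputs and is zero if follow-up tracks baseline one for one. Baseline is the mean of two collections, which lessens regression to the mean. Protocol 14.1.6.1 already allows exploratory regression adjustment.

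Most of this stands and limits the point. It does not remove it: the adjustment allowed in protocol 14.1.6.1 is optional and names no covariate, and the baseline value is already collected for every randomized patient.

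Four stronger readings are tempting, and the documents do not support them:
- *Every dropout is imputed without regard to their own level.* The other observed visits inform the imputation, so the gap matters most for patients with no post-baseline UPE.
- *The loss is the same in all four endpoints.* In the all-patients population the randomization strata separate baseline UPE below 2 g/day from 2 g/day or more, so baseline is partly adjusted there.
- *The uPCR analysis uses an untransformed baseline against a log-scale outcome.* SAP 2.9.2.4 does not state the scale of that covariate.
- *Log baseline UPE is the missing term throughout.* For uPCR and uACR the matching covariate is the measure's own log baseline.

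**Conclusion.** The point holds as one of efficiency and consistency. The time-averaged UPE ANOVA, both versions of the repeated-measures model and the FCS imputation list no baseline value, while the plan's closest comparators do.

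Over the assumed ranges the variance reduction forgone is 0% to about 16% with SD 0.63 and 0% to about 10% with SD 0.80. Mid-range values are about 5% and 3%. These figures fit the high-risk group best and should be read as upper values for the all-patients population.

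A reader might infer that the durability results would be biased, or that the primary or key secondary conclusions are at risk. Neither follows: randomization protects the unadjusted comparison, the simulation found negligible bias, and those conclusions do not use these models.

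**What to change.** - Add log baseline UPE to the time-averaged UPE model, making it an analysis of covariance.
- Add each measure's own log baseline to the repeated-measures models in SAP 2.9.2.3.2 and 2.9.2.4. A baseline-by-visit term is optional, since the primary model has none.
- Add log baseline UPE to the FCS imputation model.
- State that the baseline uPCR covariate in the time-averaged uPCR analysis is on the log scale.
- Align protocol 14.1.10.3 with these changes.

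The cost is wording in several places in the SAP and protocol, and a few degrees of freedom, which is negligible at N of 180 or more. No new data are needed. The change should be made before the interim database snapshot, by which protocol 14.1.4 requires the SAP to be final, so that the covariates are fixed before study-level unblinding.

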Natural logarithm transformation will be used to analyze 24-hour UPE, 24-hour uPCR, 24-hour uACR, spot-urine uPCR and spot-urine uACR. Geometric-mean ratio relative to the study baseline will be presented by treatment group and visit for the FAS population. A repeated measures model for the change in the log-transformed value from baseline will be used for analysis. The model will include treatment, time (as a categorical variable for the scheduled timepoints), treatment by time interaction, randomization strata as fixed effects and a time-dependent covariate for open-label treatment of narsoplimab as fixed effects, and an AR (1) covariance matrix. The time-dependent covariate is a binary variable that has a value of 0 before the initiation of the open-label treatment and 1 afterwards. It is defined for the placebo group only. The REML method will be used to estimate the model parameters. The difference in least squares (LS) means between the treatment groups and its 95% CI will be estimated for each post-baseline scheduled visit. The LS mean will be estimated with 95% CI for each treatment group. The ratio of the GMR between the treatment groups will also be estimated with 95% CI. It is noted that the primary analysis of 24-hour UPE is based on the 24-hour UPE up to Week 36 and the time-dependent covariate is not applicable to the primary analysis.

Time adjusted AUC change from baseline in spot-urine uPCR through 36 weeks will be calculated as the AUC of the change from baseline in spot-urine uPCR divided by the time from

CONFIDENTIAL

No use, disclosure, or reproduction outside of Omeros without prior written authorization

baseline to the last observation on or before Week 36. Time average of change in spot-urine uPCR will be summarized descriptively. An ANOVA model with treatment and randomization strata as covariates will be performed.

The binary endpoints will be summarized descriptively. Non-responder imputation will be used to impute missing data. Exact 95% confidence intervals for the crude rate will be calculated and a CMH test stratified by the randomization stratum will be performed for the FAS population.

The time-to-event endpoints will be analyzed by Kaplan-Meier (KM) method for each treatment group for the FAS population. Median time with 95% confidence interval will be provided by treatment group. Log-rank test stratified by the randomization stratum will be performed.

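### SAP 2.9.2.3.2 and 2.9.2.4 give two different repeated-measures models for the same five urine-protein variables and no rule on which governs, so the supportive Week 96 difference is not uniquely defined

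*SAP*

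**What the plan says.** SAP 2.9.2.3.2 opens its longitudinal paragraph with "Natural logarithm transformation will be used to analyze 24-hour UPE, 24-hour uPCR, 24-hour uACR, spot-urine uPCR and spot-urine uACR". It then sets out a REML repeated-measures model for the log change in the FAS, with treatment, visit, their interaction and the strata. On covariance it says: "Within-patient error will be modelled via an unstructured covariance matrix". It has no open-label term.

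SAP 2.9.2.4 repeats the list: "Natural logarithm transformation will be used to analyze 24-hour UPE, 24-hour uPCR, 24-hour uACR, spot-urine uPCR, and spot-urine uACR". Population, estimation method and the four basic fixed effects are the same, but the model adds "a time-dependent covariate for open-label treatment of narsoplimab as fixed effects, and an AR(1) covariance matrix". Of the covariate it says: "It is defined for the placebo-treated group only". LS-mean differences and their confidence intervals "will be estimated for each post-baseline scheduled visit", as in 2.9.2.3.2, so Week 96 is reported under both models.

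Protocol 14.1.10.3 carries only the second model: "and an AR (1) covariance matrix", with the open-label covariate likewise limited ("It is defined for the placebo group only").

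The related provisions are these:
- Protocol 10.2.8 does not restrict open-label entry by arm, and SAP 3.2.1 counts open-label use by treatment group.
- SAP 2.3 and Table 1 adopt treatment policy for the primary and key secondary endpoints.
- SAP 2.9.2.1 uses unstructured covariance for the primary MMRM and keeps AR(1) for estimation failure.
- SAP 2.9.1 makes all other efficacy endpoints supportive, outside type I error control.

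**The concern.** One endpoint has two prespecified analyses, neither ranked, so either could be reported after unblinding as the planned one.

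They do not answer the same question at Week 96. With no open-label term, the contrast compares the arms as randomized, whatever was given later. With a placebo-only term, the placebo mean is shifted to what the model predicts had nobody in that arm gone open-label, while the narsoplimab mean keeps any open-label benefit. Entry also requires high proteinuria and little reduction at Week 72, so the coefficient mixes drug effect with selection on the outcome being modelled.

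AR(1) further assumes one variance at all visits and one correlation between neighbouring visits. For the 24-hour measures the visits are Weeks 12, 24, 30, 36, 48, 72 and 96, with gaps of 6 to 24 weeks. Spot ratios are not taken at Weeks 24 and 30 (Protocol 20.2.3). At stake is the credibility of the late proteinuria summaries.

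**Working it through.** The documents give no figure for either model, so there is none to reproduce.

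**Where the models can differ.** Under the current protocol open-label treatment starts from Week 72, after the Week 72 assessment. Among the regular visits up to end of study, the covariate therefore acts only at Week 96.

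**Size of the difference.** In the second model the Week 96 contrast holds the covariate equal in both arms, so approximately

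gap = (placebo open-label share) × (size of the estimated open-label coefficient).

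Example: 0.096 × 0.467 = 0.045, against a simulated gap of 0.051.

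**Inputs from the documents.** High-risk group N = 280, 1:1 (SAP 1.3.2, 1.2). Log-scale SD 0.63 at Week 36 (SAP 1.3.1, blinded estimate). Effect of a 35% reduction, taken as ln(0.65) = −0.431 at all visits; the SAP prints −0.393, which does not matter here.

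**Assumed, not in the documents.** Dropout 0 or 15%; baseline UPE lognormal, truncated at 2 g/day; probability 0.2 or 0.65 of meeting the eGFR criterion, giving about 9% or 31% of placebo patients on open-label drug; open-label effect 0 or −0.431; Week 96 SD 0.63, 0.74 or 0.99; several correlation shapes. Both models were fitted by REML to the same data, 500–800 simulated trials per scenario.

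**Week 96 differences (log scale).**

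| Open-label effect | Placebo share | Week 96 SD | Unstructured, no term | AR(1), placebo-only term | Gap |
|---|---|---|---|---|---|
| −0.431 | 9.6% | 0.63 | −0.381 | −0.432 | 0.051 |
| −0.431 | about 31% | 0.63 | −0.28 | −0.43 to −0.45 | 0.15–0.17 |
| −0.431 | 9.4% | 0.74 | −0.379 | −0.418 | 0.039 |
| −0.431 | 30.7% | 0.74 | −0.274 | −0.398 | 0.124 |
| −0.431 | about 31% | 0.99 | −0.28 | −0.35 | 0.07 |
| 0 | 31.0% | 0.63 | −0.428 | −0.445 | 0.017 |
| 0 | 30.4% | 0.99 | −0.428 | −0.346 | 0.082, opposite direction |

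On the ratio scale, exp(−0.381) = 0.683 and exp(−0.432) = 0.649, a 32% against a 35% reduction. At 31% uptake, exp(−0.28) = 0.756 and exp(−0.43) = 0.651, or 24% against 35%.

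The last two rows isolate selection. With no open-label effect at all, the coefficient averaged −0.046 (constant variance) or +0.237 (rising variance).

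**One-arm adjustment.** In one scenario (placebo share 31.0%, constant SD) the 17.2% of narsoplimab patients who went open-label also gained −0.2. The true treatment-policy difference was −0.329, and the true difference with no open-label use in either arm was −0.431. The placebo-only model averaged −0.483, beyond both. The unstructured model averaged −0.315.

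**All-patients population.** Entry needs baseline UPE above 2 g/day. With 280 of 450 planned patients high-risk (0.62) and the same coefficient, the constant-SD gaps scale to about 0.62 × 0.05 = 0.03 and 0.62 × 0.15 = 0.09.

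**Standard error at Week 96 (model SE divided by empirical SE).** The unstructured model gave 0.95–1.01 in every scenario. The AR(1) model with the term gave 0.98–1.01 at constant variance, 0.92–0.96 if SD rises to 0.74, and 0.73–0.76 if it rises to 0.99 (for example 0.0973/0.1303 = 0.747). At constant variance, 31% share and 15% dropout, its SE was larger than the unstructured one (about 0.084–0.088 against 0.077–0.078).

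**Week 36.** The two estimates agreed to within 0.001 on average.

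**The case against.** These are supportive summaries. The named UPE secondary endpoints stop at Week 72: Week 36 in all patients follows the primary method (SAP 2.9.2.3.1), and the time averages use AUC with analysis of variance. What remains is the tertiary and exploratory change over time. This stands, and it limits the weight of the point.

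A placebo-only term also has a rationale. A placebo patient on open-label drug has crossed over, whereas a narsoplimab patient receives more of the assigned drug. SAP 2.3 fixes treatment policy only for the primary and key secondary endpoints. That is fair, but the adjusted contrast is then a different estimand, which the SAP neither names nor ranks.

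The section titles might be read as dividing secondary and exploratory endpoints from the rest. They do not: both sections list the same five variables, and SAP 2.1 has 24-hour uPCR over time as both tertiary and exploratory. The AR(1) model is also the protocol's only version, so the unstructured model is the departure. That is true, and it is why the protocol must be aligned too.

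A reader might go further and infer that AR(1) intervals are always too narrow, or that a Week 96 test runs at a raised false-positive rate. The documents do not support this. They give no Week 96 SD, the understatement vanishes at constant variance, and no error-controlled test exists at that visit. Nor do these results show that unequal visit spacing alone does harm.

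**Conclusion.** The conflict is real and follows from the text alone: one set of variables, two models, no precedence. Its consequence is that the Week 96 treatment difference depends on which section the analyst follows. At constant SD the two answers are about 0.05 log units apart at a 9% placebo open-label share and about 0.15 apart at 31%. These sizes are illustrative, because uptake and open-label effect are assumed. Entry needs three criteria and a confirmed measurement, so 31% is not a forecast.

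Understatement of the Week 96 standard error by AR(1) is a possibility, conditional on variance rising over follow-up: 4–8% at an assumed SD of 0.74 and 24–27% at 0.99.

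The Week 36 primary analysis, the named UPE secondary endpoints and the eGFR tests are not affected. This is a specification fault in supportive analyses that should be corrected before unblinding; it does not threaten the confirmatory results.

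**What to change.** - **Name one main analysis:** the 2.9.2.3.2 model, with unstructured covariance, no open-label term, and AR(1) only if estimation fails, as in 2.9.2.1. This matches the treatment-policy approach of SAP Table 1.
- **Remove the 2.9.2.4 version or relabel it** as a sensitivity analysis with its own stated estimand and the same handling of open-label use in both arms. State the covariate's coding: if it were left missing rather than set to 0 in the narsoplimab arm, PROC MIXED would drop that arm's records.
- **Align Protocol 14.1.10.3,** or record the departure from it in the SAP. Protocol 14.1.4 asks for an amendment only when a principal feature changes, which is unlikely for a supportive analysis.

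The cost is wording in both documents and more covariance parameters. Seven visits need 7 × 8 / 2 = 28, against 2 for AR(1), which is manageable with 280 to 450 patients.
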